7.9 Storage and analysis of research samples

Research samples will be collected as detailed in section 7.7 and Appendix 1. Full requirements for research sample collection and storage are detailed in the trial laboratory manual provided with the Investigator Site File.

The following blood samples will be processed by the University Hospitals of Leicester NHS Trust central pathology labs and will be collected at room temperature from the trial site. These samples will likely be taken as part of routine care at the index admission but will be considered research samples at subsequent visits. These samples are not stored for the purposes of the study and are either used or destroyed during the testing process. The results of these blood tests will be printed and stored within the Case Report Form (CRF), as well as uploaded into the database.

- Biochemistry Profile – Full (including U&E, LFTs)
- Full Blood Count (FBC)
- C-Reactive Protein (CRP)
- Trop I and BNP

The following samples will be analysed for research purposes to answer secondary outcomes and for future ethically approved research by the research team and processed at the Respiratory BRC laboratories, University of Leicester. Samples will be kept on ice or stored in monitored -20°C or -80°C freezers prior to analysis, unless contraindicated.

- Urine sample
- Sputum sample (collected on ice and processed at 4°C as soon as possible and within 2 hours of expectoration) including RNA
- Blood samples including:
 - FBC
 - Serum and plasma
 - DNA (visit 1 only) and RNA

All samples collected for exploratory future analysis will be stored within the Respiratory BRC. The Respiratory BRC is a registered Tissue Bank and all samples are stored in accordance with the Human Tissue Act 2014. Disposal will be according to local laboratory procedures.

7.10 Pandemic guidance

In the event of a pandemic (e.g. COVID-19) or local/national lockdowns which may affect COPD-HELP participants, the trial team will check ahead of scheduled trial visits that participants are able to attend in line with local NHS Trust policy. Government guidelines with regards to testing and self-isolation should be followed if a participant experiences symptoms, tests positive and/or must self-isolate. Dosing may be delayed up to 4 weeks and trial visits will be rescheduled following completion of the government required self-isolation period/a negative test.

It is unavoidable that participants will need to attend hospital in order to take part in the trial. However, the trial team will ensure participants spend the least amount of time in hospital as possible in order to reduce the risk of transmission in participants and staff. Few assessments may be performed remotely including; Quality of Life / Symptoms Assessments (eMRC; SGRO; CAT; WEMWBS; LCADL), review of concomitant medication and adverse events/SAEs.

Collection of follow up data will be consistent with clinical care without compromising the scientific validity of the trial, ensuring safety assessments and key endpoints of the trial are met.

To facilitate descriptive characterisation of participants who have not been able to undergo spirometry testing as part of the study, results from historical or contemporaneous spirometry testing performed as part of usual care will be collected from hospital and primary care records where available.

7.11 End of trial

This trial will end when the specified number of participants have been recruited, all participants have completed their last follow up visit, data validation has taken place and the database is locked and statistical analysis complete.

Data reported in the final report to REC and MHRA within 12 months of the End of Trial will include the primary and secondary outcomes (see sections 3.3.1 and 3.3.2).

Participants who become lost to Follow Up will be followed-up via their hospital records until 48 weeks to collect information on the number of exacerbations, number of hospitalisations and death. Those consented to truncated follow-up (consented to study from July 2023 onward) will be followed-up via their hospital records until their Final Follow-up visit which will occur 4 weeks \pm 7 days from what would have been their final dosing visit (based on when they are consented to the trial).

The trial will be stopped prematurely if:

- Mandated by the Ethics Committee or the Sponsor
- Mandated by the Medicines and Healthcare products Regulatory Agency (MHRA)
- Following recommendations from the Data Safety Monitoring Committee (DSMC) or otherwise the Trial Steering Committee (TSC) determine the trial should stop
- Funding for the trial ceases

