3.3.2. Secondary Outcome Measures

3.3.2.1. Exacerbations and Healthcare Utilisation

- Time from randomisation to next hospital readmission or death due to a respiratory cause
- Total number of hospital readmissions all cause up to 48 weeks
- Total number of moderate exacerbations up to 48 weeks
- Time from randomisation to treatment failure (defined as the composite of three endpoints: 1. treatment intensification with systemic corticosteroids and/or antibiotics for respiratory reasons; 2. step-up in hospital care for respiratory reasons including transfer to the intensive care unit or readmission; or 3. all-cause mortality)
- Time from randomisation to death (all cause)
- Time from randomisation to death (respiratory cause)
- Time from randomisation to next hospital readmission (all cause)
- Time from randomisation to next hospital readmission (respiratory cause)
- Time to discharge from randomisation

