7.2.1 Additional consent for biological specimens and future research

Additionally, participants will be given the opportunity to consent to access their primary care records (historical and during the trial), as well as to the storage of their biological specimens in a HTA approved bio-bank at the University of Leicester for future ethically approved research. This is optional and participants will be able to opt out of this without affecting their involvement in the trial. Both data and samples will be pseudonymised and may be transferred externally to collaborators with a further materials transfer agreement.

The research team will also seek permission to use participants' postcodes for future research investigating the link between their disease progression and the environmental pollution in the area in which they live. This will involve linking participants' health data outcomes (e.g. exacerbations) with their postcode by members of the University of Leicester. With consent, data will be transferred encrypted from the University Hospitals of Leicester NHS Trust to named individuals at the University of Leicester for analysis.

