7.8 Withdrawal criteria

Specified criteria for discontinuation of trial treatment will be for participants that miss more than one dose of the trial treatment or who delay a dose for >4 weeks. The only exception will be when this delay is due to a COPD exacerbation resulting in hospitalisation, in which instance the next dose will be administered at the next due date or as soon as possible afterwards to allow the participant to recover.

Every effort should be made by the research team to keep the participants in the trial. However, participants have the right to withdraw their consent to take part in the trial at any time without having to give a reason and this will not affect their future care. Withdrawal of consent details and reasons (if known) should be recorded on the CRF and in the medical notes.

The investigator may discontinue treatment of a participant at any time if they are not compliant with the trial protocol or to protect the participant's safety and well-being after consultation with the CI. The IMP may also be discontinued in the case of an adverse event which the investigator considers sufficient to jeopardise the safety of the participant. Participants who want to discontinue trial treatment should be encouraged to remain in the trial and

to continue to be followed-up as per the protocol or as per routine care. Participants who discontinue treatment, for whatever reason, will be asked for their consent to continue collecting data, as a minimum this must include data on hospital admissions and deaths for the remainder of the trial (48 weeks) in order to answer the primary outcome. Those declining this will be withdrawn from the trial (thus withdrawing their consent).

Every effort should be made to keep the participant in the trial to collect important efficacy and safety data. Additionally, there are a number of trial assessments (e.g. Quality of Life measures/Symptom Assessments) that may be collected over the telephone if the participant agrees to be contacted. Withdrawals from the trial should be discussed with the CI or their deputy and the Trial Manager. If a participant has withdrawn/discontinued from the trial for any reason, then his/her screening and trial ID number(s) cannot be issued to another participant.

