3.2 Secondary Outcomes

3.2.1 Definition and Derivation of Secondary Outcomes

Exacerbations and Healthcare Utilisation

- Time from randomisation to next hospital readmission or death due to a respiratory cause

The time from randomisation to next hospital readmission or death (due to a respiratory cause) is defined as a time to event outcome measured in days. The date of randomisation as well as the date of readmission or death due to respiratory causes (whichever occurs first) will be used to calculate time to event. For participants not experiencing an event the time will be calculated from randomisation until last known follow-up assessment event-free. A variable to indicate event (with a value of 1) or no event (with a value of 0) will be derived. Details of the primary outcome analysis are included in section 5.5.

- Total number of hospital readmissions all cause up to 48 weeks

The total number of hospital readmissions (all cause) is defined as a count outcome. The number of hospital readmissions (all cause) in total during the 48 (truncated follow-up

minimum 24) weeks corresponding to each participant will be calculated. Where no hospital admission have occurred a value of zero will be derived.

- Total number of moderate exacerbations up to 48 weeks

The total number of moderate exacerbations is defined as a count outcome. The severity of a COPD exacerbation will be deemed as “Moderate” if the participant required treatment with steroids or antibiotics and was not hospitalised (Oba, Y. et al, 2017).

The number of moderate exacerbations each participant had over the course of 48 (truncated follow-up minimum 24) weeks will be calculated.

- Time from randomisation to treatment failure (defined as the composite of three endpoints: 1. treatment intensification with systemic corticosteroids and/or antibiotics for respiratory reasons; 2. step-up in hospital care for respiratory reasons including transfer to the intensive care unit or readmission; or 3. all-cause mortality)

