6.5.1.3 Count Outcomes

A generalised linear model (assuming a negative binomial distribution, which accounts for variability among participants in the number of and frequency of the count variable) will be fitted for each count outcome measure with explanatory variables of treatment arm and stratification variables, and log-time on study as an offset. The offset (log-time), allows for different lengths of follow-up time for each participant (Keene et al, 2008). Time on study will be capped at 49 weeks. This assumes that missing data is missing at random (MAR), and will be applied where all of the available observed data are analysed without deletion nor imputation.

The count data is assumed to follow a negative binomial distribution with the over dispersion. If the dispersion is found to be non-significant (i.e no evidence of over-dispersion) we will consider the simpler Poisson model where the dispersion parameter equals to zero. The ratio of the rates (RR) on the intervention arm relative to placebo, associated two-sided 95% confidence interval (CI) and p-value will be reported. A value of 1.0 would indicate the same rate as placebo; the lower the ratio the greater reduction in exacerbations compared with placebo. A two-sided p-value ≤ 0.05 will be considered

as a significant difference in the number of COPD exacerbations in 48 weeks between the two treatment arms.

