6.5.3 Sensitivity Analyses

The primary analyses for all none time event outcomes (i.e continuous, binary and count outcomes) will consider any missing data to be missing at random (MAR) and complete case analysis carried out. However, if comparison of patterns of missingness and descriptive differences between treatment arms indicate this assumption is not valid, additional sensitivity analyses may be carried out and methods of imputation will be included in detail in the statistical analysis plan.

To ensure the reliability of the analysis of key secondary outcome measures, we will conduct a sensitivity analysis under various scenarios. This will involve evaluating the secondary outcomes; number of readmissions, number of exacerbations, and SGRQ (assessed for three sub-domains and the total score), to thoroughly assess the robustness of our results.

Individuals will be considered to have had some missing data for the two count variables if they have less than 47 weeks (48 weeks – 7day window) follow-up with the exception of those with planned truncated follow-up.

In the first approach, regardless of whether missingness is assumed to be random or non-random, we will perform the outlined statistical procedures. Additionally, we will provide descriptive characteristics of the missing group compared to the non-missing group, exploring potential similarities or dissimilarities between them. This comprehensive approach allows for a thorough examination of the impact of missing data on our study outcomes.

In the second approach, we are aware that throughout the trial, some participants may leave the study due to a high number of exacerbations or death before reaching their 48-week follow-up. This leads to missing data that is not at random, rendering

standard imputation methods inappropriate. Therefore, the data for key secondary outcomes for these participants will be analysed in the following way:

Pattern Mixture Model:

Robustness of the results will be assessed within the pattern mixture model. A pattern mixture model is a type of statistical model used to analyse data with missing values, especially when the missingness is not at random (MNAR).

This method is a 2-stage procedure where the 1st stage involves the use of multiple imputation to impute all missing values assuming data are “missing at random”.

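### Moderate exacerbations cannot be reliably seen through hospital-record or minimum-data follow-up, yet the SAP gives them the same undefined observation time and completeness rule as readmissions

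*Protocol*

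**What the plan says.** The outcome is a listed secondary one, "Total number of moderate exacerbations up to 48 weeks" (Protocol 3.3.2.1). SAP 3.2.1 classes an exacerbation as moderate "if the participant required treatment with steroids or antibiotics and was not hospitalised".

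Three routes supply data once a participant leaves the normal visit schedule:

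- **Lost to follow-up (Protocol 7.11).** Such participants "will be followed-up via their hospital records until 48 weeks to collect information on the number of exacerbations, number of hospitalisations and death". Those on truncated follow-up "will be followed-up via their hospital records until their Final Follow-up visit".
- **Stopped treatment but still in the trial (Protocol 7.8).** Participants are asked to agree to continued data collection, and "as a minimum this must include data on hospital admissions and deaths for the remainder of the trial (48 weeks").
- **Primary care records (Protocol 7.2.1).** Access is sought for the past and for the trial period, but "This is optional and participants will be able to opt out of this". Protocol 11.1 plans to request primary and secondary care data, without naming them as the source for this count.

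On analysis, SAP 6.5.1.3 fits each count outcome with "explanatory variables of treatment arm and stratification variables, and log-time on study as an offset", capped at 49 weeks. SAP 6.5.3 treats participants as having some "missing data for the two count variables if they have less than 47 weeks" of follow-up, and exempts those with planned truncation. Neither section says when time on study ends for someone followed only through hospital records or the minimum data set.

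**The concern.** Hospital records suit admissions and deaths. They cannot be relied on to show a course of steroids or antibiotics given in the community, which is what makes an exacerbation moderate. Protocol 7.11 lists exacerbations separately from hospitalisations, so it appears to expect that count from a source that cannot reliably give it.

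The two count outcomes can therefore be observed for different lengths of time in the same person, while the SAP gives them a single clock. What is at stake is the moderate-exacerbation rate in each arm, possibly the rate ratio, and whether the right people enter the missing-data sensitivity analysis. SAP 6.5.3 treats the number of exacerbations as a key secondary outcome. SAP 6.5.1 makes the modified intention-to-treat analysis the main one for these counts, so the problem sits in the main analysis of this outcome.

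**Working it through.** **The plan's own figures.** The documents give no moderate-exacerbation rate, no power for that outcome and no loss-to-follow-up rate. The only attrition figure is the 5% in Protocol 10.1, which means recruited but never dosed. The sample size is not in dispute and reproduces: the Freedman formula with HR 0.6, two-sided 0.05 and power 0.8 gives 126 events. The mepolizumab event proportion is 1 − 0.35^0.6 = 0.467 and the average with 0.65 is 0.559, so N = 226. Then 226/0.95 gives 238.

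**One clock, two outcomes.** Take a participant last seen at week 12 and then followed in hospital records to week 48, with a constant event rate and no moderate exacerbations visible in those records.

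| Time on study ends at | Moderate exacerbations | Readmissions |
|---|---|---|
| Week 48 (end of records) | 12 weeks of events over 48 weeks of exposure: 12/48 = 25% of the true rate; passes the 47-week rule | Events and exposure match |
| Week 12 (last assessment) | Events and exposure match; flagged as incomplete | Either 36 weeks of usable data are dropped, or 48 weeks of events sit over 12 weeks of exposure (48/12 = 4 times the true rate) |

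Neither choice serves both outcomes.

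**Effect on the rate if the unobserved time is in the offset.** Let f be the share of participants who move to records-only or minimum-data follow-up, w the week this happens, and c the share of moderate exacerbations still captured. All three are assumptions. With a constant rate and 48 weeks of planned follow-up:

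observed rate / true rate = 1 − f × (48 − w)/48 × (1 − c)

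- f = 10%, w = 24, c = 0: 1 − 0.10 × 0.5 = 0.95
- f = 10%, w = 24, c = 0.5: 1 − 0.10 × 0.5 × 0.5 = 0.975
- Mildest case examined (5%, week 36, c = 0.5): 1 − 0.05 × 0.25 × 0.5 = 0.994
- Most severe case examined (30%, week 12, c = 0): 1 − 0.30 × 0.75 = 0.775

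**Effect on the rate ratio.** Observed ratio = true ratio × (mepolizumab factor)/(placebo factor). With a true ratio of 0.80, w = 24 and c = 0:

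| Lost, placebo | Lost, mepolizumab | Factors (mepolizumab/placebo) | Observed ratio |
|---|---|---|---|
| 20% | 20% | 0.90/0.90 | 0.80 |
| 20% | 10% | 0.95/0.90 | 0.844 |
| 10% | 20% | 0.90/0.95 | 0.758 |

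Equal loss leaves the ratio alone and lowers both rates. Unequal loss can hide benefit or exaggerate it. If the offset stops when ascertainment stops, the factor is 1.00 in each arm, given that the unobserved time is missing at random.

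**The case against.** The strongest reply is that no passage says records-only time counts as event-free. A reader might infer that it does, but time on study is simply not defined for these participants. Where the SAP does define an end, it uses the last assessment: for time-to-event outcomes (6.4.1) and for AE and SAE rates (3.2.1). SAP 6.5.1.3 also says that the offset is there to allow for differing follow-up. If the statistician stops the clock at the last assessment, the moderate rate is not diluted. That stands, and makes the bias conditional. It does not remove the problem, because that choice mishandles readmissions found later in the records that Protocol 7.11 says will be searched.

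Four other inferences are tempting, and the documents do not support them:

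- **That the sensitivity analysis cannot correct the problem.** For participants who leave because of many exacerbations or death, SAP 6.5.3 keeps the observed count and, in its second approach, imputes the remaining time at the control rate, though nothing past death. What remains is that a participant whose records-only time counts as follow-up can reach 47 weeks and not be flagged.
- **That the SAP expects more placebo patients to leave.** SAP 6.5.3 says only that some participants may leave, and names no arm.
- **That the ratio could move past 1.** From 0.80 with 5% of mepolizumab person-time unobserved, reaching 1 needs 0.80 × 0.95 = 0.76 = 1 − f, so 24% of placebo person-time, or 48% of placebo patients lost at week 24. Nothing in the documents suggests loss on that scale.
- **That treatment failure has the same blind period.** SAP 3.2.1 measures participants without the event to their last event-free assessment, and 6.4.1 censors those lost at the last assessment.

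There are also mitigations. The per-protocol count analysis (SAP 6.5.2) ends exposure four weeks after the last dose and largely avoids the issue, though it is secondary. Protocol 7.8 encourages full follow-up after stopping treatment, and telephone contact is allowed. Some participants will consent to primary care access.

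**Conclusion.** The mismatch between source and definition is real, and so is the gap in the analysis rule. After loss to follow-up, or under minimum-data follow-up, moderate exacerbations are not reliably observed, and the SAP does not say when their time at risk ends or whether such time counts toward 47 weeks. A single clock is wrong for one of the two counts whichever way it is read.

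The size cannot be fixed from the documents, because they give no loss rate. Under the stated assumptions, including the unobserved time leaves the moderate rate at 0.95 of its true value with 10% lost at week 24, within an examined range of 0.775 to 0.994. The rate ratio moves only with differential loss or capture, in either direction: 0.80 to about 0.84 or about 0.76 in the scenarios shown. Partial capture in hospital records or through primary care would shrink these effects.

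This concerns one secondary count and, on the other reading of the clock, the readmission count. Admissions and deaths suit hospital records, so the primary outcome is not affected by this mismatch. It should be settled before database lock.

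**What to change.** In SAP 3.2.1, 6.5.1.3 and 6.5.3, define a separate observation time for each count outcome:

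- **Readmissions:** to the end of hospital-record follow-up (week 48, or the planned Final Follow-up in the truncated cohort).
- **Moderate exacerbations:** to the last visit or telephone contact at which steroid and antibiotic courses were reviewed, or to the end of primary care record coverage where the participant consented to access.

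Use each outcome's own time in its offset, and apply the 47-week rule to that time. In Protocol 7.11, state that hospital-record follow-up supplies hospitalised exacerbations only.

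The cost is SAP and protocol wording and one extra derived date. That date should be available from data already collected, since concomitant medication is reviewed at every follow-up visit (Protocol 7.7.2 to 7.7.4). The moderate-exacerbation analysis will have slightly less person-time. Sample size, treatment and visits do not change.
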